Trial Protocol

Title: "Longitudinal trial assessing cellulite in women wearing a new compression garment - one side with ink printed micro-pads ("Vari-pads") and one side without."

Principal Investigator: [name] MS FRCS(Gen) FCPhleb

Protocol Identifying Number: TWC-SM-2023-01

Protocol version number & date: v 1.1 28 June 2023

Ethics: Not required according to HRA Decision Tools (see Result - England Ethics 21-May-

2023) – and confirmed by e-mail from MHRA.

NCT: To be registered on ClinicalTrials.gov on confirmation of Ethics position

Background:

Cellulite is a very common condition that affects up to 90% of women.¹ It is much less commonly found in men. It presents as a dimpling principally of the skin of the buttocks and thighs, with the appearance having been described as resembling "orange peel", "cottage cheese" or a "quilt". In women who are affected, it usually appears after puberty. It occurs in all races, but is thought to occur more commonly in Caucasians.¹

The product being tested:

The product being tested is to be a retail (non-medical) product presented as standard compression shorts with a pattern of small, raised pads ("Vari-pads") of different heights printed on the inner aspect. A previous trial that we have performed has suggested that wearing these for eight hours a day can reduce the appearance of cellulite.² In addition, subjects found these compression pants to be very comfortable.²

In this trial, we want to see whether the subjective and objective improvement is due to the compression alone, or whether the Vari-pads on the inside of the product enhance the subjective or objective impression of cellulite. As such, we have asked the manufacturer to produce pairs of pants where the Vari-pads are printed onto the inner aspects as per usual on one side only, but not on the other side.

Subjects will then be asked to wear the apparel for at least eight hours a day, at times most suitable for themselves.

If and when they notice a difference between the appearance of cellulite between the two sides, they will notify us and we will then swap them into the 'normal' garments with Vari-pads on both sides, which they are then welcome to continue to wear.

Subjects:

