- 4] Variable end-point visit whenever the subject can tell that there is a difference between the left and right sides if the subject does not reach this end point, they will only have 3 visits and will not need the garment with Vari-pads on both sides.

First Visit (day zero):

Subjects will be asked to sign a consent form if they have asked sufficient questions and have decided to go ahead with the trial.

- Their cellulite will be graded as per the Nürnberger F, Müller grading system³

Grading	Description
Scale	
0	No alteration to the skin surface - NO CELLULITE SO THESE
	SUBJECTS will be EXCLUDED
1	Skin is smooth whilst subject is standing/lying, but alterations can be seen
	by pinching the skin, or by muscle contraction
2	'Orange-peel' or mattress appearance is evident upon standing without the
	use of any manipulation (pinching or muscle contraction)
3	Alterations seen in grade two presented together with raised areas and
	nodules

- Standard high-resolution photographs will be taken of their buttocks from behind, side and obliquely in the standing position with the muscles relaxed. The same will then be performed for the thighs. [Subjects will not be photographed in any way so as to be able to identify them.]
 - Subjects will have height and weight measured and noted.
- Localised transcutaneous water content measurement using LymphScanner (Delfin Technologies, Finland) this is a non-invasive device passed over the skin to determine the electrical conductance of the skin and sub-cutaneous tissues.
- They will be given a Celluqol[®] Quality of life questionnaire (long version see appendix)⁴ to complete.
- They will then be given the garment (x2) with one side covered with the Vari-pads, with the other side without any raised pads.

Variable End-point Visit:

When subjects can see or feel a significant difference in the cellulite of their buttocks and/or thighs between the sides, they will contact us and return for assessment.

At this visit, the following will be performed:

- Weight
- Photographs
- Questions as to the routine of garment wearing how many hours per 24 and when
- Transcutaneous water content buttocks and thighs
- Celluqol® QOL Questionnaire
- They will be given 2 new garments with Vari-pads on BOTH sides.

3 Months Visit.

At this visit, the following will be performed:

- Weight
- Photographs
- Questions as to the routine of garment wearing how many hours per 24 and when
- Transcutaneous water content buttocks and thighs

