- Cellugol® QOL Questionnaire

6 Months Visit - end of trial and £100 paid if all visits completed. The subject can keep the x2 bilaterally padded garments.

At this visit, the following will be performed:

- Weight
- Photographs
- Questions as to the routine of garment wearing how many hours per 24 and when
- Transcutaneous water content buttocks and thighs
- Celluqol® QOL Questionnaire

Primary endpoint:

- The time taken for patients to notice a self-determined significant difference between their right and left side and request the full garment.

Secondary endpoints:

- Quality of life changes by Celluqol® questionnaire 0, 3 and 6 months.
- Changes in photographs 0, 3, 6 months as assessed by 2 'blinded' observers
- Changes in transcutaneous water measurements

Interim Analysis:

We will perform an initial analysis when all of the results are in from the 1 month and 3 months visit.

Consent form: Please see attached.

Subject information sheet: Please see attached.

Insurance: The Whiteley Clinic has full insurance cover for clinical trials.

Payment: Subjects who complete the trial to 6 months will be allowed to keep the compression garments (worth £90.00 each) and will be given £100 in compensation for their time and travel.

References:

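### The blinded photograph reading omits the visit at which the self-judged primary event is declared, so women who declare before 3 months have no blinded post-baseline reading under one-sided wear

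*Protocol*

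**What the plan says.** **The event.** Under Primary endpoint, the protocol measures the time for a woman to "notice a self-determined significant difference between their right and left side and request the full garment". The Variable End-point Visit is triggered "When subjects can see or feel a significant difference in the cellulite of their buttocks and/or thighs between the sides". No examiner confirms the event. She wears raised pads on one side only, and the protocol describes no masking of her.

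**What follows a declaration.** The Variable End-point Visit lists weight, photographs, wear questions, water content and the questionnaire. Its last item is: "They will be given 2 new garments with Vari-pads on BOTH sides". For a woman who never declares, the list of visits says "they will only have 3 visits and will not need the garment with Vari-pads on both sides".

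**The blinded reading.** Secondary endpoints assigns two blinded observers to changes in photographs at 0, 3 and 6 months. The variable end-point photographs are not included.

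**What is kept.** The product section says "we will then swap them into the 'normal' garments with Vari-pads on both sides, which they are then welcome to continue to wear". The 6 Months Visit section lets the subject retain two bilaterally padded garments and does not restrict this to declarers. Payment says "Subjects who complete the trial to 6 months will be allowed to keep the compression garments (worth £90.00 each", with no type or number given. The £100 is paid on completing all visits.

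**The concern.** The trial asks whether the pads add anything to compression alone, and the within-woman comparison of sides is its means of answering. That comparison is intact only while one side is unpadded. The primary event rests on the judgement of a wearer who can tell which side is padded, so a blinded look at the same skin at the same moment is the natural check. The protocol takes those photographs but leaves them out of the blinded reading. For early declarers, whose events would count most in favour of the product, every blinded post-baseline photograph is taken after both sides have become padded.

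Declaring also brings two full garments. If what a woman keeps depends on declaring, the outcome and a reward are linked. The sections on retention do not settle whether it does.

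**Working it through.** **1. Blinded readings under one-sided wear**

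Inputs: blinded readings at 0, 3 and 6 months (Secondary endpoints); photographs at day zero, the variable end-point, 3 months and 6 months (visit sections); bilateral garments issued at the variable end-point visit, listed after the photographs. Assumptions: the visit follows its listed order, and the new garments are worn from then on.

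| Declares | Planned post-baseline readings under one-sided wear | With the variable end-point set added |
|---|---|---|
| Before 3 months | 0 of 2 | 1 of 3 |
| Between 3 and 6 months | 1 of 2 | 2 of 3 |
| Never | 2 of 2 | 2 of 2 |

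For the first row, the variable end-point set is the only post-baseline set taken under one-sided wear.

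**2. Gross value of declaring, for a 6-month completer**

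Inputs: £90 per garment and £100 cash (Payment); two garments issued at day zero and two more on declaring (First Visit, Variable End-point Visit). A bilateral garment is taken as £90. The one-sided garment is not priced separately, so it is given an assumed value £v, from £0 to £90. The £100 cancels, because a non-declarer has only three visits to complete.

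- A, all issued garments kept: (100 + 180 + 2v) - (100 + 2v) = £180.
- B, only bilateral garments kept, and only declarers have them: (100 + 180) - 100 = £180.
- C, true swap with the first pair handed back, non-declarers keeping theirs: (100 + 180) - (100 + 2v) = 180 - 2v. This is £0 at v = 90, £90 at v = 45 and £180 at v = 0.
- D, 6 Months Visit sentence taken literally, every completer keeping two bilateral garments: (100 + 180) - (100 + 180) = £0.

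The range is £0 to £180, but its ends are not equally supported. A fits poorly with the swap in the product section and with the two garments named at 6 months. B conflicts with Payment, which lets every completer keep garments. Payment attaches £90 to completers' garments generally, and a non-declarer holds only one-sided ones, so v = 90 is the most natural value and C then gives £0.

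The gain is also gross: a declarer makes 4 visits and a non-declarer 3, for the same £100. No formula above contains the time of declaring.

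**The case against.** **Restricting the blinded reading to three time points contradicts nothing, and supporting analyses may sit in an SAP that is not shown.** The first part is true. But the protocol itself fixes the time points, so this is a stated choice that can be judged as it stands.

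**Photographs are a weak check.** This stands in part. The event may be felt rather than seen. Grade 1 is defined as "Skin is smooth whilst subject is standing/lying, but alterations can be seen" only on pinching or contraction, whereas photographs are taken "in the standing position with the muscles relaxed". Lack of visible support cannot disprove an event.

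**Water content is measured at the variable visit, and that endpoint is not tied to 0, 3 and 6 months.** Also true. However, the protocol does not say that readings are recorded by side, and the measure does not replace a blinded view of appearance.

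**The retention texts are ambiguous more than contradictory.** Largely so: if each completer keeps what she holds at the end, much of the conflict goes. What remains is that the 6-month sentence is not limited to declarers, the product section sets no completion condition, and the fate of the one-sided pair is not stated.

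**A stronger inference.** A reader might infer that women are paid £180 to declare, and to declare early, so that the primary endpoint is biased. The documents do not support this. The £180 needs one of the less natural interpretations or a worthless one-sided garment. The garment value is the same whenever she declares. The extra visit is unpaid. The information sheet, attached but not shown, may settle retention.

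**Conclusion.** The photograph point holds. Women who declare before 3 months have 0 of 2 blinded post-baseline readings under one-sided wear, although suitable photographs are taken. For them the blinded endpoint cannot address pads against no pads during one-sided wear, nor check the declared event. This rests on the bilateral garments being issued after the photographs and worn from then on. The number of women affected depends on when they declare, which the protocol does not predict. The change is cheap and should be made.

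The garment point is secondary. The gross gain from declaring lies between £0 and £180, with £0 the better supported end, and it is offset by an extra visit. It is a possible incentive to declare. It is not a monetary incentive to declare sooner, no effect on event times is shown, and no size of bias can be derived. Earlier use of the full garment is a separate, non-monetary attraction.

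**What to change.** **1. Read the variable end-point photographs.** Add them to the work of the two planned observers. Mask the observers to padded side and visit, and present each woman's sets in random order without visit labels. In every set, including day zero, have them score which side looks better (left, right or no difference), and derive change from day zero after unblinding. If the padded side is the same for all women, the masking is weak and the report should say so.

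Leave the primary endpoint unchanged. As a supporting analysis, report how many declared events are visibly supported on the padded side and how many favour the unpadded side, separately for grade 1 and grades 2 to 3, with the caveat on felt and grade 1 differences. Also report how many women already look better on the padded side at day zero, since they cannot score a gain.

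Cost: at most 60 x 2 = 120 extra readings, plus the side score on sets already planned. If day-zero sets must be re-read for side, that is a further 60 x 2 = 120. No new photographs, visits or observers are needed.

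**2. Reconcile the product section, the list of visits, the 6 Months Visit section and Payment.** State the number and type of garments a 6-month completer keeps, make this independent of declaring, and tell subjects. If every completer received a bilateral pair, the total is at most 60 x £180 = £10,800 at stated value. The net extra is £180 per completer who did not declare, for example £3,600 if 20 did not (an assumed number). A uniform return rule would avoid that cost but would change the Payment promise and remove a reward for completing. Neither choice removes the attraction of getting the full garment earlier.
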